5.5 Follow-up

Safety Follow-Up Visit

Patients have to be evaluated for symptoms and adverse events in a visit 30 days (+/- 7 days) after permanently stopping study treatment. This contact may be completed via

telephone. The following assessments should be performed:

A radiological tumor assessment using the RECIST criteria, version 1.1 (see

Appendix 5) must be performed if only it weren't performed at the end of

treatment visit.

(CT scan of the abdomen, pelvis and chest or hepatic MRI and CT scan of the

pelvis and chest without injection).

Tumor markers: CEA (Carcino-Embryogenic Antigen), CA 19.9 (Carbohydrate

Antigen 19-9) if not done at the EOT visit

Concomitant medications (including anti-cancer medication)

Adverse events documentation

Follow-up every other month until Death

Vital status

Anti-cancer medications

Telephone follow-up is acceptable. Site staff must use caution when contacting the patient's family for this information, especially if they are no longer under the care of the investigator,

so as to not inadvertently cause any distress to the family of a patient who is no longer alive.

6. Treatments

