2.2.2 Secondary endpoints

The secondary efficacy endpoints include:

- Progression-free survival (PFS), defined as the time (days) from date of randomization to date of first observed disease progression (investigator's radiological or clinical assessment) or death due to any cause, if death occurs before progression is documented. Patients without tumor progression or death at the time of analysis will be censored at their last date of tumor assessment.
- Time to Deterioration is defined as the time between the date of randomization and the first time the patient has a WHO \geq 2 during treatment.
- Disease control rate (DCR), defined as the rate of patients, whose best response was not progressive disease (i.e., CR, PR or SD), to all randomized patients in the treatment group-Objective response rate (OOR), defined as the rate of patients with CR or PR, to all randomized patients in the treatment group. Patients prematurely discontinuing without an assessment will be considered non-responders for the analysis.

- Safety will be evaluated by clinical and biological means and scored on the NCI-CTCAE version 5.0 scale, performed at each visit (every 2 weeks).
- -Quality of life will be evaluated, based on the EORTC QLQ-C30 questionnaire (appendix 2).

[figure not shown]
3. Experimental plan

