5.1 Tabulated overview

Tabulated overview NEXT-REGIRI	Screening					Regorafenib (1 cycle = 4 weeks (1 cycle = every 15 days and 1 cycle = every 4 weeks)						Evaluation (Every 8 weeks)	End of treatment	Safety Follow-up ^c .	Follow-up	End of study
Baseline Documentation	As early as second- line	~ 28 days	Within 28 days	Within 14 days	Within 7 days	CX D1ª	C1, C2 D8	CX D1 ^a	C1, C2 D8	Cx D15	C1, C2 D22	~8 weeks	~14 days	~30 days	Follow-up: every other month	
Molecular testing informed consent	Х															
Clinical trial informed consent			Х													
Complete medical history			Х													
Inclusion/Exclusion Criteria			Х													
Physical examination					Χ	Χ		Χ		Χ			Χ			
β-HCG blood test					Χ	Χ		Χ								
Status of Ras, Raf and MSI have to be known		Χ														
Laboratory Studies																
12-lead ECG					Χ	X ¹		X ¹				Х	X ⁴			
Complete blood count					Χ	Χ		Χ		Χ			X ⁴			
Coagulation					Х	Х		Х		Х			X ⁴			
Electrolyte panel					Х	Х		Х		Х			X ⁴			
Chemistry panel					Χ	Х		Х		Х			X ⁴			

							,	Treatment							
Tabulated overview NEXT-REGIRI		Screening				Regorafenib (1 cycle = 4 weeks		e = every 15 d	EGIRI lays and 1 cy eeks)	cle = every 4	Every 8 weeks	End of treatment b,e	SafetyFollo w-up ^{c-d}	Follow- up	End of study
Liver function test panel				Х	X ²		Х	Χ	Χ	Х		X ⁴			
Thyroid function				Χ	Χ		Χ					X ⁴			
Tumor markers				Χ	X ³		X ³				Χ	X ⁴	X ⁵		
Urinary analysis				Χ	Χ		Χ		Χ			X ⁴			
Imaging assessments															
Radiologic Tumor assessment d		Х									Χ	X ⁶	X ⁵		
Other Clinical Assessments															
ECOG				Х	Х		Х		Χ			X ⁴			
Body weight, BSA, height, and vital signs				Х	Х		Х	X ⁷	Χ			X ⁴			
Concomitant medications			Х		Х		Χ		Χ			Χ	Х		
Adverse events				Χ	Χ		Χ	Χ	Х	Χ		Χ	Χ		
Drug dispensing					X8		X8								
Drug accountability					X8		X8		Χ			Х			
Post-study survival status														Х	
Anti-cancer medications														Х	
Patient's diary					X ⁹		X ⁹		Χ						
Patient Reported Outcomes															
Quality of life questionnaires					X ¹⁰		X ¹⁰				Χ				
Phone call : adverse events, blood pressure					Х	Х				X					
Ancillary study															
Immunohistochemistry ^e															X

- a: Cycle 1 Day 1 : the laboratory evaluations are not required at day 1 of cycle 1 if those were completed within 7 days
- b: Within 14 days (+/- 7 day) after study treatment has stopped
- c: Within 30 days (+/- 7 day) after study treatment has stopped

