- Chemistry panel: albumin, lipase, phosphate, glucose, serum creatinine, clearance calculated according CKD-EPI (appendix 7)
- Hepatic panel: Aspartate Amino-Transferase (AST), Alanine Amino-Transferase (ALT), bilirubin (total and direct), GGT, alkaline phosphatase, Lactic Dehydrogenase (LDH)
- Urine analysis by urinary dipstick. If results of protein ≥ 3+, then quantification of proteinuria on a 24-hour urine collection must be done.
- Drug accountability (pharmacy)
 Verify patient's diary. It will allow to patient to write down his oral intakes and blood pressure values

The following assessments should be performed on day 15 of cycle 1 and 2:

Stivarga® (Regorafenib - arm B):

• these laboratory evaluations are required: Aspartate Amino-Transferase (AST), Alanine Amino-Transferase (ALT), bilirubin (total and direct)

The following assessments should be performed on day 22 of cycle 1 and 2:

REGIRI (arm A):

- Phone call by a treatment nurse for knowing if there are any adverse events and blood pressure value (current state of the art)
- These laboratory evaluations are required: Aspartate Amino-Transferase (AST),
 Alanine Amino-Transferase (ALT), bilirubin (total and direct)

The following assessments should be performed at each evaluation i.e (every 8 weeks):

REGIRI or Regorafenib:

 Tumor markers CEA (Carcino-Embryogenic Antigen), CA 19.9 (Carbohydrate Antigen 19-9)

 Radiological tumor assessment using the RECIST criteria, version 1.1 (see Appendix 5) must be performed. (CT scan of the abdomen, pelvis and chest or hepatic MRI and CT scan of the pelvis and chest without injection)

A PET scan is not acceptable for radiological evaluation. Throughout the study, the identical lesions to those identified and measured at baseline must be evaluated using the same technique, and preferably by the same radiologist. Copies of all CT scans performed for tumor assessment in non-progressive enrolled patients will be stored on CDs at the site

 EORTC QLQ-C30 (appendix 2) questionnaires will be completed by the patient at each evaluation i.e 8 weeks

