5.4 End of treatment Visit

When a patient is taken off treatment, the following assessments should be performed within 14 days after study treatment has stopped provided the last clinical and laboratory

evaluations > 7 days.

- Physical examination with weight, BSA and vital signs (heart rate, blood pressure)
- ECOG performance status
- Adverse events documentation (including Start/Stop dates, seriousness, CTC notation and grading, relationship to study drug, outcome and action taken) using CTCAE V5.0
- Concomitant medications
- 12 lead ECG

- A CBC with differential should be performed: RBC, hemoglobin, hematocrit, platelet count and WBC. WBC must include differential neutrophil, lymphocyte, monocyte, basophil and eosinophil counts
- Coagulation panel: Prothrombin time (PT) or the International Ratio of PT (PT-INR) and Partial Thromboplastin Time (PTT)
- Electrolyte panel: sodium, potassium, chloride and calcium
- Chemistry panel: albumin, lipase, phosphate, glucose, serum, creatinine, clearance calculated according CKD-EPI (appendix 7)
- Liver function test panel: Aspartate Amino-Transferase (AST), Alanine Amino-Transferase (ALT), bilirubin (total and direct), GGT, alkaline phosphatase, Lactic Dehydrogenase (LDH)
- Thyroid function test: TSH, free T3, and free T4
- Tumor markers: CEA (Carcino-Embryogenic Antigen), CA 19.9 (Carbohydrate Antigen 19-9)
- Urine analysis by urinary dipstick. If results of protein ≥ 3, then quantification
 of proteinuria on a 24-hour urine collection must be done
- A radiological tumor assessment using the RECIST criteria, version 1.1 (see Appendix 5) must be performed if the last radiological assessment > 1 months. (CT scan of the abdomen, pelvis and chest or hepatic MRI and CT scan of the pelvis and chest without injection)
- Drug accountability (pharmacy)

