ANC < 1500/mm ³	J21*	No dose modification + G-CSF

Protocole NEXT-REGIRI -Version 6.0 du 09/11/2023

Page **44** sur **86**

and Platelets > 100 000/mm ³		
Platelets < 100 000/mm ³	121*	Padusa by 1 dosa laval
Whatever the number of ANC	JZ I"	Reduce by 1 dose level

^{*} or until 28th day as needed (maximum)

Modalities of Reintroduction of treatment : ANC \geq 1500/mm³ and Platelets \geq 100 000/mm³ If the Platelets and/or ANC values are not correct at D28, the patient will discontinue permanently the study treatment.

At the time of Nadir

In the case of a grade 4 neutropenia, whatever the duration or complication i.e by an infection or fever > 38°5, the G-CSF will be administered at the next course of treatment. If the same toxicity continues with G-CSF then the irinotecan dose will be reduced at the dose immediately inferior. If there is a third occurrence of this toxicity, the patient will permanently discontinue the study treatment.

Table 5: Action and dose modification during the administration of Regorafenib in case of hematological toxicity

Hematological toxicity (Modification dose/delay for Regorafenib)			
Grade	Treatment delay	Dose modification	
Grade 0-2	No delay in Regorafenib	No modification dose	
Grade 0-2	treatment	No modification dose	
Grade 3	No delay in Regorafenib	Reduce by 1 dose levelbc	
Grade 3	treatment	heduce by Tuose level	
	Interrupt Regorafenib		
Grade 4	until hematologic	Reduce by 1 dose level ^{bc}	
	toxicity resolves to	heduce by Tuose level	
	Grade ≤ 2ª		

a If no recovery within 30 days, the treatment will be permanently discontinued.

- b If more than 2 dose reductions are necessary, the treatment will be permanently discontinued.
- c Cf table a.

Table 6: Action and dose modification during the administration of Regorafenib in case of non-hematologic toxicity

Non-hematological toxicity (dose modification/delay for Regorafenib) (except hand-foot skin reaction, hypertension, liver function test abnormalities and diarrhea)^a

Grade	Treatment delay	Dose modification
Grade 0-2	No delay in Regorafenib treatment	No dose modification
Grade 3	Interrupt Regorafenib until non hematologic toxicity resolves to Grade ≤ 2 ^b	Reduce by 1 dose level ^{cd}
Grade 4	Discontinue treatment permanently	Discontinue treatment permanently

- a In the absence of nausea/vomiting prophylaxis and diarrhea not treated.
- b If more than 2 dose reductions are necessary, the treatment will be permanently discontinued.

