	occurence	permanently	
> 20 times ULN (Grade 4)	Any	Discontinue regorafenib	
	occurence	permanently	
> 3 times ULN (Grade 2 or higher) with	Any	Discontinue regorafenib	
concomitant elevation of bilirubin > 2 times	occurence	permanently	
ULN		Control liver function every	
		week until resolution or	
		return to baseline	

Termination of Regorafenib:

- -In the event of gastrointestinal perforation or fistula develops
- -In the event of reversible Posterior Encephalopathy Syndrome (REPS)
- -In the event of the appearance of cardiac ischemia and/or infarction

Other toxicities

The other toxicities will have to manage symptomatically, if possible. For any toxicity grade \geq 2 at D15 except alopecia and anemia, the irinotecan will be delayed up to two weeks and the toxicity will have to be grade \leq 1 to perform the course.

ARM B: STIVARGA® (REGORAFENIB)

Dosage changes should be made in 40 mg increments (1 tablet). The recommended daily dose of Regorafenib is 160 mg.

Dose reductions of Stivarga ®
1st reduction: 120 mg
2 nd reduction: 80 mg

Table b

Table 10: Dose modification/Delay for toxicities related to study drug (except handfoot Skin reaction and hypertension)^a

NCI-CTC V5.0	Dose	Dose Modification	Dose for Subsequent Cycles
	Interruption		
Grade 0-2	Treat on time	No change	No change
Grade 3	Delay until <	Reduce 1 dose level ^c	If toxicity remains < Grade 2,

Protocole NEXT-REGIRI -Version 6.0 du 09/11/2023

Page 52 sur 86

	Grade 2 ^b		dose re-escalation can be
			considered at the discretion
			of the treating investigator.
			If dose is re-escalated and
			toxicity (Grade 3) recurs,
			institute permanent dose
			reduction.
Grade 4	Delay until <	Reduce by 1 dose level ^c .	
	Grade 2 ^b	Permanent discontinuation	
		can be considered at	
		treating investigator's	
		discretion.	

a Excludes alopecia, non-refractory nausea/vomiting, non-refractory hypersensitivity and asymptomatic laboratory abnormalities.

Table 11: Dose modifications for hand-foot skin reaction

Skin Toxicity Grade	Occurrence	Suggested Dose Modification
Grade 1: Numbness,	Any	Maintain dose level and institute immediately
dysesthesia, paraesthesia,		supportive measures for symptomatic relief
tingling, painless swelling,		
erythema or discomfort of		
the hands or feet which		
does not		
disrupt the patient's normal		
activities		
Grade 2: Painful erythema	1st	Decreasing dose by one dose level and institute
and	occurrence	immediately supportive measures.

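### After the exit scan no progression date is scheduled, yet any later death counts as a PFS event, so unrecorded progression lengthens PFS and can distort the arm comparison

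*Combined protocol and SAP*

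**What the plan says.** Section 5.3 puts the RECIST scan in the treatment period, under "The following assessments should be performed at each evaluation i.e (every 8 weeks". Section 5.4 asks for a scan at the end-of-treatment visit that "must be performed if the last radiological assessment > 1 months". Section 5.5 adds one at the 30-day visit that "must be performed if only it weren't performed at the end of" treatment. Read together, these give each patient who stops one exit scan.

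Section 5.5 then sets "Follow-up every other month until Death", with two items (vital status and anti-cancer medications), and allows it by telephone. Table 5.1 agrees: its follow-up column marks "Post-study survival status" and anti-cancer medications, and nothing on progression.

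Section 2.2.2 defines a PFS event as progression, by the investigator's radiological or clinical assessment, or "death due to any cause, if death occurs before progression is documented". It sets no limit on the time between the last assessment and that death. Patients alive without progression are censored at their last tumour assessment. Section 8.1 keeps patients who stop treatment in the trial and asks for unspecified clinical-event data up to the last scheduled follow-up; it does not name progression. Section 9.3 gives PFS a stratified log-rank test, an HR, and 3- and 6-month estimates, and leaves the SAP to be written before database lock.

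**The concern.** Section 8.1 lists several reasons for stopping treatment without progression, including adverse events, interruptions longer than 4 weeks and non-compliance. If such a patient progresses after the exit scan, no scheduled item records it. When the patient dies, the PFS event takes the date of death.

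If later progressions go unrecorded, two things follow:

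- **No true effect:** the HR favours the arm with more stops without progression.
- **True effect:** even equal stopping tends to pull the HR toward 1 and cost power, because time after progression is added to both arms.

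Equal stopping cannot be taken for granted, because the arms have different stop rules in section 6.3. At grade 4 non-haematological toxicity, outside its listed exceptions, table 6 (arm A) requires a permanent stop. Table 10 (arm B) leaves a permanent stop to the investigator's discretion.

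PFS is the first-listed secondary endpoint. A later SAP can add analyses, but it cannot supply dates that nobody collected.

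**Working it through.** **The plan's own figure.** Section 9.1 sizes the trial on OS only. By Schoenfeld's formula, events = 4(1.960 + 0.8416)² / (ln HR)² = 31.396 / (ln HR)².

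- HR 7/15: 31.396 / 0.5809 = 54.05, so 55.
- HR 0.47: 31.396 / 0.5701 = 55.07, so 56.

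The stated 55 is reproduced, and it does not depend on progression dates. The plan states no PFS effect, event count or power.

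**Where a progression date can come from**

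| Period | Scheduled scan | Progression item |
|---|---|---|
| On treatment (5.3) | every 8 weeks | yes, from the scan |
| End of treatment (5.4) | if the last is over 1 month old | yes, from the scan |
| 30-day visit (5.5) | if not done at end of treatment | yes, from the scan |
| Two-monthly until death (5.5, table 5.1) | none | none |

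**Inputs from the documents.** 39 patients per arm; accrual over 64 months plus 5 (January to June 2025); scans every 8 weeks. PFS medians of 1.9 to 3.7 months come from the earlier sorafenib trial (section 1).

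**Assumptions.** Exponential PFS with median 2 or 3 months; in the true-effect case 3.5 v 2.0 months, HR 2.0/3.5 = 0.57. Mean survival after progression 4.5 or 6.5 months. 10% to 30% of an arm stops without progression, early (0.5–2.5 months) or spread over time. The exit scan falls 0–5 weeks after the stop. Later progression is recorded in 0, 50 or 90% of cases and dated within 2 months. Otherwise PFS = time to progression + survival after progression. An unrecorded case therefore gains 4.5 or 6.5 months on average, against a PFS median of 2 to 3 months.

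**Simulation results** (HRs from 150,000–200,000 patients per arm; power and false wins from 2,000 trials of 39 v 39 in each of four settings, unstratified log-rank)

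| Quantity | Stops, A v B | None recorded | Half | 90% |
|---|---|---|---|---|
| HR, no true effect | 20% v 10% | 0.92–0.98 | 0.95–0.99 | 0.99–1.01 |
| | 30% v 10% | 0.85–0.95 | 0.91–0.99 | 0.98–1.01 |
| | 10% v 30% | 1.05–1.18 | 1.02–1.09 | 0.99–1.01 |
| One-sided false win (nominal 2.5%) | 30% v 10% | 8.7–10.1% | 4.6–5.9% | 2.8–3.1% |
| HR, true effect (0.58 with no stops) | 10% v 10% | 0.61–0.63 | 0.60–0.61 | 0.58 |
| | 20% v 20% | 0.63–0.66 | 0.61–0.63 | 0.59 |
| Two-sided power (63–66% with no stops) | 10% v 10% | 53–59% | 56–62% | 64–65% |
| | 20% v 20% | 44–54% | 52–57% | 61–64% |

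The no-effect HR ranges cover two codings of the exit scan and two readings of the stop share (patients who actually stop before progression, or patients assigned a stop time). The other rows use the actual-stop share.

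**Sensitivity to the model.** A second model used the design's OS medians (15 v 7 months) and PFS medians of 3.7 v 2.1 months, with none recorded.

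- No true effect: HR 0.92 at 30% v 10% and 1.10 at 10% v 30%, inside the ranges above.
- True effect: HR moves from 0.61 to 0.57 at 30% v 10%, and from 0.61 to 0.67 at 10% v 30%.
- True effect, equal stops of 10% or 20%: only from 0.61 to 0.62.

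Giving arm A longer survival after progression in the first model leaves 0.61 and 0.63 at equal 10% and 20% stops. The equal-stop shift is therefore the least certain figure.

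**Six-month PFS, median 2 months.** The last 8-weekly scan before 6 months is at week 24, or 24 × 7 / 30.44 = 5.52 months. With all progressions recorded, the estimate is 0.5^(5.52/2) = 15%. With 10% stops and none recorded it reads 17–18%.

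**Affected patients.** At 10%, 20% and 30% stops, 3.9, 7.8 and 11.7 of 39 stop without progression. With none recorded, PFS events that are deaths more than 16 weeks after the last scan number 2.2–2.6, 4.3–5.2 and 6.6–7.8.

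**Sampling error.** With about 76 PFS events, SE(log HR) = √(4/76) = 0.23. The half-recorded HR of 0.91 is a shift of 0.09 on the log scale.

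**The case against.** The strongest reply is that the effect depends on two rates the documents do not give, and that having none of the later progressions recorded is an extreme case. Section 2.2.2 accepts clinical progression, section 8.1 keeps collecting clinical events, and a new anti-cancer drug reported at a two-monthly contact should prompt a question about progression. The eCRF is not in the file and may hold such a field. At 90% recorded the bias is negligible. This stands as a limit on size. It does not close the gap, because the operative lists in 5.5 and table 5.1 omit progression and 2.2.2 gives new therapy no role in PFS.

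Other points also stand:

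- One difference in stop rules cannot support 30% v 10%. Arm B takes regorafenib on 21 days per cycle against 14 in arm A, so either arm could stop more.
- The plan sets no PFS power, so the 63–66% baseline is a constructed benchmark.
- The true-effect model does not match the 15 v 7 month OS design, and a model that does gives a smaller equal-stop shift.
- Some dates can still be retrieved from hospital records, so the loss need not be total.
- Counting death without a time limit is not itself an error. The difficulty is its pairing with follow-up that schedules no progression item.

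**Conclusion.** The concern holds. Followed as written, the protocol dates an unrecorded post-treatment progression at death, and this can distort the PFS HR and raise the 3- and 6-month estimates.

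Under the assumed 30% v 10% stopping and no true effect, the expected HR is 0.85–0.95 with nothing recorded and 0.91–0.99 with half recorded. It is close to 1 with 90% recorded. With a true effect and equal stopping, the shift toward 1 runs from about 0.01 to 0.08 with nothing recorded, depending on the model and stop share.

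Stop and capture rates are assumptions, and the favoured arm is not established. Half-recorded shifts lie well inside sampling error. Only patients who stop without progression are affected; OS and its 55 events are not. The point is worth acting on because the correction is small and must be made while dates can still be collected.

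**What to change.** 1. In section 5.5 and table 5.1, add one item to the two-monthly follow-up, repeated until progression is recorded: progression yes/no, date, and method (radiological or clinical, from routine care). Complete it retrospectively from records where possible. No extra scan is needed.
2. Report by arm how many patients stopped without progression, and how many PFS events are deaths more than 16 weeks after the last tumour assessment.
3. Optionally, specify in the SAP a sensitivity analysis that censors those deaths at the last adequate assessment. Keep the 2.2.2 definition as the main analysis.

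The cost is one field on an existing contact and two counts in the report, with no new visits. Routine-care dates will be less regular than 8-weekly scans.

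The censoring analysis can err the other way. With no true effect and 30% v 10% stops it gives HR 1.09–1.11 if nothing is recorded. With 90% recorded it gives 1.01–1.02, against 0.98–1.00 for the main analysis in the same coding. The SAP should say so and should not present the two analyses as bracketing the truth.

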6.1 Experimental treatment or procedures

Experimental arm: REGIRI (arm A)

[figure not shown]

Figure 1: REGIRI regimen

The treatment schedule will be as follows:

- Starting on days 1 and 15 of each 28-day cycle, all patients will receive irinotecan as an intravenous infusion over a 90 minute period.

The initial dose of irinotecan will be 120 mg/m².

The dose for the second infusion of irinotecan will be 150 mg/m² over 90 minutes if no diarrhea of grade >1 NCI-CTCAE V 5.0 grading or others toxicities of grade >2 occur.

The dose for the third and subsequent infusions of irinotecan will be 180 mg/m² over 90 minutes under the same conditions as for the 2nd infusion.

- -On days 2–8 and 16–22 of each cycle, all patients will receive Regorafenib 160 mg orally once daily.
- -A chemotherapy course = 15 days, 1 cycle = 4 weeks

Control arm: Stivarga® (Regorafenib) (arm B)

-Regorafenib will be given orally at a dose of 160 mg once daily over 3 weeks then one week off.

1 cycle = 4 weeks

[figure not shown]

Figure 2: Regorafenib schedule

The following products will be used in the study:

- Regorafenib, 40 mg tablets
- Irinotecan, 180 mg/m² IV (20 mg/ml)

ARM A: REGIRI (Regorafenib + Irinotecan)

Irinotecan

See manufacturer's product information (Appendix 8).

Irinotecan will be prescribed by each center and used in its marketed form.

The irinotecan will be diluted in a 5 % glucose solution or a 0.9% sodium chloride solution. The irinotecan will be delivered over 90 minutes as an intravenous infusion.

Regorafenib

For Packaging, List of excipients and Storage: See Investigator's brochure (Appendix 8).

Regorafenib® will be provided by Sponsor as tablets of 40 mg.

The investigational product(s) label will bear sponsor's name, address and telephone number, the EudraCT number, product name, dosage form and strength, quantity of investigational product par container, batch number, expiration date, dosing instructions, required storage conditions and required caution statements and/or regulatory statements as applicable.

Protocole NEXT-REGIRI -Version 6.0 du 09/11/2023

Page 39 sur 86

Receipt, distribution, return and destruction (if any) of the study drug must be properly documented.

To have complete control over the distribution and use of the study drug, the drug accountability must be performed on Day 1 of each cycle starting on Cycle 2. Bottles must be returned to the Investigator with all unused medication. Throughout the study, all unused study medication will be accounted for. The information will be recorded in the drug dispensing log.

The study drug must be exclusively used for the investigation specified in this protocol, and it will only be accessible to authorized staff. The sponsor delegate labelling, packaging and shipping of product during the study to Sodia. Our partner Bayer will send Regorafenib to Sodia which deliver Regorafenib to the investigational site's pharmacy on behalf of sponsor. The renewal of the Regorafenib must be requested by fax or e-mail to Sodia by the investigator center.

Regorafenib will be orally administered. It must not be chewed or smashed.

It should be taken once daily in the morning from day 2 to day 8 and day 16 to day 22 of cycle, at the same hour as possible, with approximately 200 mL of water. The Regorafenib can be administered after a low-fat (<30% fat) meal.

The Investigator or designated study personnel is responsible for dispensing the study drug to patients.

ARM B: Stivarga® (Regorafenib)

See manufacturer's product information (Appendix 8).

Stivarga® will be delivered in retail pharmacies and used in its marketed form.

To have complete control over the use of the study drug, the drug accountability must be performed on Day 1 of each cycle starting on Cycle 2. Bottles must be returned to the Investigator with all unused medication. Throughout the study, all unused study medication will be accounted for Investigator or pharmacist.

Regorafenib will be orally administered. It must not be chewed or smashed.

It should be taken once daily in the morning during the first 21 days of cycle, at the same hour as possible, with approximately 200 mL of water. The Stivarga® (Regorafenib) should be administered after a low-fat (<30% fat) breakfast.

